7.3.2 Risk Assessment

- **7.3.2.1** There is a potential risk for loss of confidentiality in this study which will be minimalized by only the research team accessing the research data and the PHI.
- **7.3.2.2** Unique patient study specific identifiers will be used during data collection.
- **7.3.2.3** All data forms will be maintained in a locked cabinet in the research coordinator's office.
- **7.3.2.4** No PHI will be transferred, shared or stored on personal computers.
- 7.3.2.5 Risk of exposure for X-rays; but the dose involved in general x-rays is minimal.
- **7.3.2.6** There are no increased risks associated with the control arm of the study, which is a traditional non-weight-bearing period of 6 weeks following foot and ankle surgery. The risks associated with the study arm, which is immediate weightbearing following foot and ankle surgery, include potential pain with weightbearing on the surgical extremity; potential wound complications associated with the surgical incision sites; possible hardware failure; possible non-union, mal-union, or delayed union during osseous healing; and/or possible non-healing or delayed healing of soft tissue structures.
- **7.3.2.7** Currently, the post-operative course following foot and ankle surgery is subjective, based on the previous experiences of the surgeon performing the surgery. We do not believe that there is any additional risk associated with the control arm of the study, which is to maintain non-weightbearing for 6 weeks following foot and ankle surgery. All of the potential risks, including pain, non-union, non-healing, infection, wound complications, and others are possible regardless of the post-operative course. Additionally, we believe that the risks associated with immediate weightbearing following foot and ankle surgery are minimal, as there is ample evidence of previous success with immediate weightbearing following certain procedures.
- **7.3.2.8** We will minimize the risk of harm by close follow-up during the post-operative course, utilizing appropriate protective devices during weightbearing following foot and ankle surgery, and thoroughly educating our participants on the warning signs of potential complications, regardless of the study group into which the participant falls.

7.3.3 Potential Benefits of Study Participation

The potential benefits of study participation, namely for those participant randomly placed in the immediate weightbearing group of the study, would be those similar to benefits found in previous immediate or early weightbearing studies performed and mentioned in the literature review. These potential benefits would include:

- 1. The ability to bear weight on the surgical extremity in a protective boot.
- 2. Reduced muscle atrophy of the surgical extremity
- 3. Reduced stress on the non-surgical extremity
- 4. Reduced necessity of rehabilitation following healing of the surgical extremity
- 5. Increased quality of life during healing following foot and/or ankle surgery
- 6. Earlier return to work following foot and/or ankle surgery

7.3.4 Risk-Benefit Assessment

The risks of immediate weightbearing following foot and ankle surgery are not unlike the risks faced with a traditional post-operative course of non-weightbearing. While there may be a minimal increase in risk for complications in the study group, given the potential increase of stress on the fixation constructs, potential tension to the surgical incision, and potential pain associated with weightbearing immediately after surgery, we believe that the benefits outweigh the risks. Increasing quality of life during the post-operative period, while decreasing debility and returning patients to their pre-injury or pre-surgical state sooner than previously expected is a substantial benefit.

7.4 Recruitment Strategy

Patient recruitment will be generated from the clinic sites listed in section 3.2 of the protocol. Initial recruitment of study participants will be at the discretion of the participating surgeons, as they will be involved in the decision to proceed with surgery, along with the patient. Study participation will in no way affect the surgical decision making of the surgical provider. Informed Consent/Assent and HIPAA Authorization

7.5 Payment to Subjects/Families

Subjects will not be paid for participation in the study. All treatments, exams, radiographs and visits are considered standard of care with the exception of the questionnaires which will be distributed at five of their visits.

7.5.1 Reimbursement for travel, parking and meals

Discounted parking will be provided to those subjects/patients that come to the West Penn Hospital clinical site. All other sites provide free parking.

8 PUBLICATION

Principal Investigator and Co-Investigators are part of the AHN and will have complete access to all data for the purpose of publication at study completion. No other outside entities are involved in this research study.

APPENDIX

Append relevant information.

- I. DATA COLLECTION FORMS
 - a. See attached
- II. APPENDIX
 - a. Questionnaires

DATE:		VISIT: Pre-Op F/U: #1 #2 #3 #4 #5
PTID#		DATE OF SURGERY:
STUDY GROUP:	Immediate Weightbearing	Non-Weightbearing
AGE	GENDER	R M F BMI
HISTORY OF SM	IOKING None Previou	us Current If yes, how many packs/day?
HISTORY OF DI	ABETES Yes No	If yes, last A1c value?
	S:	
RADIOGRAPHIC	C/ADVANCED IMAGING FINDING	: Pre-Op #1 #2 #3 #4 #5
XRAY:		
CT:		
MRI:		Procedure(s):
MRI: Pre-Op:	VAS:	Procedure(s): 1 st MPJ fusion DMO 1 st TMT fusion
MRI: Pre-Op:		Procedure(s):
MRI: Pre-Op: AOFAS: Follow-up Visit	VAS: #2 (6-8 weeks Post-Op):	Procedure(s): 1 st MPJ fusion DMO 1 st TMT fusion
MRI: Pre-Op: AOFAS: Follow-up Visit	VAS:	Procedure(s): 1 st MPJ fusion DMO 1 st TMT fusion LisFranc ORIF Midfoot fusion 5 th met ORIF
MRI: Pre-Op: AOFAS: Follow-up Visit	VAS: #2 (6-8 weeks Post-Op):	Procedure(s): 1 st MPJ fusion DMO 1 st TMT fusion LisFranc ORIF Midfoot fusion 5 th met ORIF TNJ fusion STJ fusion PCDO PMGL
MRI: Pre-Op: AOFAS: Follow-up Visit AOFAS:	VAS: #2 (6-8 weeks Post-Op):	Procedure(s): 1 st MPJ fusion DMO 1 st TMT fusion LisFranc ORIF Midfoot fusion 5 th met ORIF TNJ fusion STJ fusion PCDO PMGL Achilles repair FHL transfer FDL transfer
MRI: Pre-Op: AOFAS: Follow-up Visit AOFAS: Follow-up Visit	VAS: #2 (6-8 weeks Post-Op): VAS:	Procedure(s): 1 st MPJ fusion DMO 1 st TMT fusion LisFranc ORIF Midfoot fusion 5 th met ORIF TNJ fusion STJ fusion PCDO PMGL Achilles repair FHL transfer FDL transfer Peroneal repair ATT transfer PTT repair
MRI: Pre-Op: AOFAS: Follow-up Visit AOFAS: Follow-up Visit	VAS: #2 (6-8 weeks Post-Op): VAS: #4 (12 months Post-Op):	Procedure(s): 1 st MPJ fusion DMO 1 st TMT fusion LisFranc ORIF Midfoot fusion 5 th met ORIF TNJ fusion STJ fusion PCDO PMGL Achilles repair FHL transfer FDL transfer Peroneal repair ATT transfer PTT repair Fibula ORIF Tibia ORIF Bimal ORIF
MRI: Pre-OD: AOFAS: Follow-up Visit AOFAS: Follow-up Visit	VAS: #2 (6-8 weeks Post-Op): VAS: #4 (12 months Post-Op):	Procedure(s): 1 st MPJ fusion DMO 1 st TMT fusion LisFranc ORIF Midfoot fusion 5 th met ORIF TNJ fusion STJ fusion PCDO PMGL Achilles repair FHL transfer FDL transfer Peroneal repair ATT transfer PTT repair Fibula ORIF Tibia ORIF Bimal ORIF Ankle fusion TAR
MRI: Pre-Op: AOFAS: Follow-up Visit AOFAS: Follow-up Visit	VAS: #2 (6-8 weeks Post-Op): VAS: #4 (12 months Post-Op): VAS:	Procedure(s): 1 st MPJ fusion DMO 1 st TMT fusion LisFranc ORIF Midfoot fusion 5 th met ORIF TNJ fusion STJ fusion PCDO PMGL Achilles repair FHL transfer FDL transfer Peroneal repair ATT transfer PTT repair Fibula ORIF Tibia ORIF Bimal ORIF Ankle fusion TAR

TID#:		Date:	
	AOFAS Ankle-Hindfoot Scale (100	Points Total)	
1. Pain (40 points)			
	None	40	
	Mild, occasional	30	
	Moderate, daily Severe, almost always present	0	
2. Function (50 point	nts)		
Activity limitation	ns, support requirements		
No limitations, no su	t		10
No limitations, no su No limitations of dail	pport y activities, limitation of recreational a	ctivities no support	10
	ational activities, cane	curries, no support	4
	daily & recreational activities, walker, c	rutches, wheelchair, bra	
4-6 blocks 1-3 blocks			4 2
Less than 1 block			0
Walking surfaces			
No difficulty on any s	urface		5
Some difficulty on uneven terrain, stairs, inclines, ladders			
Severe difficulty on uneven terrain, stairs, inclines, ladders			
Gait abnormality	,		
None, slight			8
Obvious			4
Marked			0
5	flexion plus extension)		
Sagittal motion ()	ction (30° or more)		8
Normal or mild restri			
	(15° - 29°)		4

IRB#2018-XXXWPH: Immediate Weightbearing vs. Non-Weightbearing after Foot & Ankle Surgery: A Prospective Analysis

SF-36® Health Survey Scoring Demonstration

This survey asks for your views about your health as it pertains to your hindfoot fusion.

Answer every question by selecting the answer as indicated. If you are unsure about how to answer a question, please give the best answer you can.

1. In general, would you say your health is:

Excellent	Very good	Good	Fair	Poor
0	0	0	0	0

2. Compared to your pre-operative state, how would you rate your health in general now?

Much better	Somewhat better	About the same	Somewhat worse now	Much worse now
o	0	0	Ö	O

3. The following questions are about activities you might do during a typical day. Does your health now limit you in these activities? If so, how much?

		Yes, limited a lot	Yes, limited a little	No, not limited at all
а	Vigorous activities, such as running, lifting heavy objects, participating in strenuous sports	0	0	0
ь	Moderate activities, such as moving a table, pushing a vacuum cleaner, bowling, or playing golf	0	0	0
с	Lifting or carrying groceries	0	0	0
d	Climbing several flights of stairs	0	0	0
е	Climbing one flight of stairs	0	0	0
f	Bending, kneeling, or stooping	0	0	0
g	Walking more than a mile	0	0	0
h	Walking several blocks	0	0	0
i.	Walking one block	0	0	0

#2018-XXXWPH Version 1.0 _12/2018

1

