The subjects will be identified/recruited during clinic hours as patients requiring an elective or traumatic foot and ankle surgery. During the clinic hours the primary investigator and/or the co-investigator will obtain full consent from the patient. We will recruit a minimum of 115 participants into each of two study arms, an immediate weight-bearing arm and a non-weight-bearing arm, so 230 participants will be included. Patients will be eligible if they are undergoing elective or traumatic foot and ankle surgery. Exclusion criteria will include any patient less than 18 years of age & over 89, history of foot or ankle surgery on the surgical limb, any degree of diagnosed peripheral neuropathy or peripheral vascular disease, infection, and/or unwillingness to participate at random in one of the two study arms.

Study Interventions and Measures:

We will be assessing the difference in two groups; immediate protected weight-bearing in a CAM walking boot vs strict non-weight-bearing for 6 weeks following foot and ankle surgery. Monitoring will be done by way of clinical follow-up, serial radiographs and/or other appropriate imaging modalities, and patient reported outcomes by way of AOFAS and SF-36 surveys.

Surgical procedures performed on patients included in the study will vary, as will the outcome measures for each procedure. Osseous fusions, including both elective joint fusions and bone healing following trauma, will be assessed by both clinical and radiographic evaluation. Soft tissue procedures, including elective stabilization and traumatic soft tissue repairs, will be assessed clinically and with imaging modalities

deemed appropriate. Complications during the perioperative and post-operative periods, such as non-union, infection, etc. will be included in the outcomes. All participants will also complete AOFAS and SF-36 surveys in the pre-operative and post-operative periods. We will also include return to work, activity, sport, etc. where appropriate.

Study Phase	Screening	Surgery	Post-op 2-3 w	Post-op 6-8 w	Post-op 3 m	Post-op 6 m	Post-op 1 yr	Post-op 2 yr	Unscheduled Visits
Visit Number	1		2	3	4	5	6	7	
Informed									
Informed Consent/Assent	x								
Review Inclusion/Exclusion									
Criteria	х								
Randomization	x								
Demographics/PMH	x								
Physical Examination	x		x	x	x	x	x	x	x
Adverse Event Assessment			x	x	x	x	x	x	x
Radiographs/Imagining	х		x	x	x	x	x	x	x
Complete AOFAS/SF- 36 survey	x			x	x		x	x	

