3.3 Study Population

3.3.1 Inclusion Criteria

- 1) Males or females age 18 to 89 years
- 2) Undergoing foot and ankle surgery
- 3) Must be able to read and understand English and consent for themselves

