4 STUDY PROCEDURES

4.1 Screening Visit

Below is a list of all of the procedures to be performed at each visit.

- Informed Consent
- Physical Exam
- Radiographic/Advanced Imaging
- Medical Record Review
 - Review of the medical record will include reviewing the past medical and surgical history, laboratory values, and most recent visits to other health care providers in the standard fashion of any office or inpatient encounter
- Surgical procedure discussed and operative consent
- Pre-operative AOFAS and SF-36 surveys completed

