5.1.4 AOFAS and SF-36 survey

Standardized and validated surveys to assess patient function and satisfaction. The SF36 has proven useful in surveys of general and specific populations, comparing relative burden of diseases, and in differentiating the health benefits produced by a wide range of different treatments. In this study we will use the SF36 to assess patient's perceptions of their health.

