6.1 Primary Endpoint

The primary outcome measures are the American Orthopaedic Foot and Ankle Society (AOFAS) Ankle-Hindfoot Scale score and the SF-36 Health Survey Score as it pertains to the patient's ankle/foot. These assessments will be given to the patient in the pre-operative and post-operative periods.

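### The appendix SF-36 form asks about a hindfoot fusion, contradicting the ankle/foot primary endpoint and the open eligibility criteria, and its item 2 has no referent at screening

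*Combined protocol and SAP*

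**What the plan says.** **The form.** The appendix contains one SF-36 form, under this trial's title. Its instruction reads "This survey asks for your views about your health as it pertains to your hindfoot fusion". Item 2 opens "Compared to your pre-operative state" and asks for a rating of health now.

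**The endpoint.** Section 6.1 names two primary outcome measures, the AOFAS Ankle-Hindfoot score and "the SF-36 Health Survey Score as it pertains to the patient's ankle/foot". Section 6.5 bases the sample size on both and also ties the SF-36 to the foot or ankle. Section 5.1.4 describes the instruments as "Standardized and validated surveys to assess patient function and satisfaction".

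**The population.** Section 3.3.1 requires only "Undergoing foot and ankle surgery". The abstract says "Patients will be eligible if they are undergoing elective or traumatic foot and ankle surgery" and adds "Surgical procedures performed on patients included in the study will vary, as will the outcome measures for each procedure". Section 6.4.1 expects various procedures with possibly small numbers in each. Against these, section 6.3 says that the study isolates patients having a hindfoot fusion.

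**The timing.** Section 4.1 lists "Pre-operative AOFAS and SF-36 surveys completed" at the screening visit. Section 6.4.1 gives screening as one of the visits compared in the one-way and two-way repeated-measures ANOVAs of the SF-36.

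**The concern.** The instruction line tells patients what to have in mind when they answer. A patient who has had an Achilles repair or fibula fixation is asked about an operation that was not done. That patient may rate general health, the foot, or something else, and the choice may differ between patients and between visits. The component and subdomain scores then do not clearly measure what section 6.1 says they measure.

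Item 2 has a separate problem. At screening the patient is in the pre-operative state, so there is nothing to compare it with.

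Noise of this kind that falls equally on both arms does not favour either arm, but it shrinks the standardised difference and lowers power. That matters here because the objective in section 2.1 accepts similar results as a success, and a noisier score makes the arms look more alike.

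**Working it through.** **1. Form against endpoint.** Sections 6.1 and 6.5 refer to the foot or ankle; the form refers to one operation. The two differ for any patient without a hindfoot fusion.

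**2. Form against population.** The data collection form in the appendix lists 21 procedures:
- Clearly hindfoot fusions: TNJ fusion and STJ fusion, 2/21 = 9.5%.
- With ankle fusion counted as well: 3/21 = 14.3%.
- The other 18 or 19 include first MPJ and midfoot fusions, fracture fixation, tendon repairs and transfers, and ankle replacement.

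These are shares of form entries. The field allows several procedures per patient, the table was read from a damaged layout, and no case mix is given, so the figures do not convert into shares of patients.

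**3. Which population statement stands.** The abstract, section 3.3.1, section 6.4.1 and the data collection form all describe a mixed population; section 6.3 alone describes hindfoot fusions. The weight of the text points to section 6.3 as the inconsistent one. If section 6.3 did govern, the form's instruction would suit the population, but it would still differ from section 6.1, and item 2 would still have no meaning at screening.

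**4. Screening.** The survey is completed before surgery (section 4.1), and previous surgery to the surgical limb is an exclusion (section 3.3.2). No patient therefore has a fusion on the study limb at that visit. Section 6.4.1 does not say how item 2 enters any score, so how far item 2 alone affects the screening scores cannot be stated.

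**5. The plan's own figure.** Inputs from section 6.5: d = 0.40, two-sided alpha 0.05, power 80%, 100 per group.
- Normal approximation: n = 2(1.960 + 0.842)² / 0.40² = 15.70 / 0.16 = 98.1, so 99 per group.
- Power at 100 per group: Φ(0.40 × √(100/2) − 1.960) = Φ(0.868) = 80.7%.
- Noncentral t: n = 99.08, so 100 per group; power at 100 is 80.4%.

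The stated figure reproduces, and correcting the form does not change it.

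**6. Illustration only.** Assume that the unclear referent adds random error equally in both arms, so that d becomes 0.40 × √R, where R is the reliability relative to a clean form. Power is Φ(d√50 − 1.960) at 100 per group.

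| R (assumed) | d | Power |
|---|---|---|
| 1.0 | 0.400 | 80.7% |
| 0.9 | 0.379 | 76.5% |
| 0.8 | 0.358 | 71.6% |
| 0.7 | 0.335 | 65.8% |

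The documents give no value for R. The table shows the direction and how sensitive power would be; it does not estimate the loss.

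**The case against.** **The effect on answers may be small.** The phrase appears once, in the instruction. The visible items do not repeat it: item 1 asks about health in general, and item 3 asks whether health limits listed activities. The form also tells unsure patients to give their best answer, which works against any inference that items will be skipped. This stands. The documents show the contradiction but not its effect on scores.

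**Most patients cannot be said to be affected.** A reader might infer from 18 or 19 of 21 entries that 86-90% of patients get the wrong instruction. The documents do not support that, because the entries are labels without frequencies. What they do support is that patients without a hindfoot fusion are eligible and expected.

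**The line need not be wrong for everyone at screening.** A reader might infer this because no operation has yet taken place. But section 4.1 puts discussion of the operation at the same visit, and a patient scheduled for a hindfoot fusion can read the line as the planned operation. The firmer screening defect is item 2.

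**The form shown may not be the form used.** It is headed as a scoring demonstration, carries a placeholder IRB number and is marked version 1.0 of 12/2018, while the protocol is dated 04/29/2019. This also stands, and makes confirming the version the first step. It does not remove the contradiction, since this is the only form the protocol presents.

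**Conclusion.** The point holds as a contradiction within the documents that affects a primary instrument. The form's instruction disagrees with the endpoint in sections 6.1 and 6.5 and with the eligibility criteria, and item 2 cannot be answered meaningfully at screening. Both conclusions rest on the text alone.

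The consequence for the trial is likely to be an unclear referent and some added noise in the SF-36 scores. That assumes the form shown is the one used and that patients follow its instruction. A reader might infer from the table a power of about 72-77% in place of 80%; that range rests wholly on assumed values of R from 0.8 to 0.9, and nothing in the documents supports choosing them.

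Correction is worthwhile because it is cheap and because answers given under the present wording cannot be collected again.

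**What to change.** 1. Confirm which SF-36 version patients receive.
2. Adopt one instruction that is valid before and after surgery and matches the endpoint. There are two ways:
   - Refer to the patient's foot or ankle at every visit, in line with section 6.1. This is still a modified instruction, and section 5.1.4 should say so.
   - Use the survey's unmodified instruction, and amend sections 6.1 and 6.5 so that the endpoint is no longer tied to the foot or ankle.
3. Correct section 6.3 so that it agrees with the abstract, section 3.3.1 and the data collection form. Changing the form alone would leave the conflict over the population in place.
4. Do not analyse item 2 at screening.
5. If the present form has already been used, record the version at each visit, because a patient may complete one version at screening and another later. Add a sensitivity analysis with version as a visit-level covariate. A linear mixed model handles a covariate that changes within a patient more readily than the planned repeated-measures ANOVA.

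The cost is a corrected form, matching text edits, an IRB notification and, if needed, one version field and one extra analysis. Sample size and visit schedule do not change.
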